7.4. Early Termination of Study

The study may be terminated at any time by the sponsor if serious side effects occur, if potential risks to study participants are identified, if the investigator does not adhere to the protocol, or if, in the sponsor's judgment, there are no further benefits to be achieved from the study. In the event that the clinical development of the study product is discontinued, the sponsor shall inform all investigators/institutions and regulatory authorities.

8. TREATMENT OF SUBJECTS

8.1. Identity of Study Product and Comparator

The identity of the study product and comparator are presented in [Table 4](#).

Table 4. Study Product and Comparator			
Study Product	Dosage Form	Strength	Dose
Visible Fluorescent Injectate	Solution for injection	35 mg FD001/12 mg FD003	3 mL + 1 mL for every 40 kg increase in body weight (refer to Table 7.2)
Comparator			
Omnipaque 300 (iohexol)	Solution for injection	647 mg of iohexol equivalent to 300 mg of organic iodine/1 mL	5 mL

VFI will be sourced by FAST BioMedical. The VFI is packaged in a 10-mL, 20-mm clear glass vial with a 20-mm gray stopper and blue cap, and the product is a deeply colored lyophilized cake.

Iohexol will be sourced by the VA. Iohexol is packaged in a clear 10 mL bottle with a brown cap, and the product is a colorless to pale-yellow liquid. Each mL of iohexol solution contains 1.21 mg tromethamine and 0.1 mg edetate calcium disodium.

8.2. Treatments Administered

Each subject/patient will receive 2 doses of VFI and 2 doses of iohexol, which will be administered IV through a bolus injection. An IV catheter will be inserted into the subject's arteriovenous fistula or graft by an experienced dialysis nurse.

Patients will receive 1 dose of VFI and 1 dose of iohexol approximately 4 hours prior to undergoing dialysis followed by a second dose of VFI and second dose of iohexol approximately 1 hour after completing dialysis.

The dose of VFI will be 3 mL for subjects/patients ≥ 40 and ≤ 100 kg and will increase by 1 mL for every 40 kg increase in body weight as outlined in [Table 5](#).

Body weight		Dose (mL)	VFI (mg)	FD001 (mg)	FD003 (mg)	VFI (mg/kg)	FD001 (mg/kg)	FD003 (mg/kg)
(lbs)	(kg)							
88	40	3	47.01	35.01	12	1.18	0.88	0.300
154	70	3	47.01	35.01	12	0.67	0.50	0.171
220	100	3	47.01	35.01	12	0.47	0.35	0.120
223	101	4	62.68	46.68	16	0.62	0.46	0.158
309	140	4	62.68	46.68	16	0.45	0.33	0.114
311	141	5	78.35	58.35	20	0.56	0.41	0.142
397	180	5	78.35	58.35	20	0.44	0.32	0.111
399	181	6	94.02	70.02	24	0.52	0.39	0.133
485	220	6	94.02	70.02	24	0.43	0.32	0.109
487	221	7	109.69	81.69	28	0.50	0.37	0.127
573	260	7	109.69	81.69	28	0.42	0.31	0.108
575	261	8	125.36	93.36	32	0.48	0.36	0.123
661	300	8	125.36	93.36	32	0.42	0.31	0.107
664	301	9	141.03	105.03	36	0.47	0.35	0.120
750	340	9	141.03	105.03	36	0.41	0.31	0.106

A low-protein snack will be served prior to administration of VFI (eg, toast, bagel, Graham crackers, or primarily carbohydrate-based small portion). Water will be allowed as desired up to 1.5 liters, but must be tracked on the CRF. Meals appropriate for the patient’s medical condition will be served.

8.3. Method of Assigning Subjects to Cohorts

Eligible subjects/patients will be enrolled in a single cohort.

8.4. Measurements of Compliance

Study product and comparator will be administered by qualified healthcare professionals at the study site as designated by the investigator. Details regarding dosing, including the dose administered and the date and time of dosing, will be recorded.

8.5. Storage, Accountability, and Preparation

8.5.1. Storage Conditions

The VFI will be stored in a refrigerator set to maintain 2°C to 8°C (36°F to 46°F). Vials and glass or polymer bottles of iohexol will be protected from strong daylight and direct exposure to sunlight and will be stored at controlled room temperature at 20°C to 25°C (68°F to 77°F); excursions are permitted to 15°C to 30°C (59°F to 86°F).

The VFI will be prepared within 60 minutes prior to dosing, and the prepared product will be stored at room temperature (approximately 20°C to 25°C). The product will be protected from sunlight and ultraviolet light until dosing.

Iohexol will be drawn into a syringe for administration and stored at room temperature (approximately 20°C to 25°C).

8.5.2. Preparation

The procedure for reconstitution of the FAST VFI is located in [Appendix A](#).

8.6. Packaging and Labeling

8.6.1. Study Product

The study product will be provided with appropriate labeling, including: sponsor name, address, and phone number, product name, active constituents, content by volume and number of units, batch number, expiry date, storage instructions, and the term “Caution: Investigational Device. Limited by US Federal Law for Investigational Use Only.”

8.6.2. Blinding of Treatment Assignment

Not applicable. This is an open-label study.

8.7. Concomitant Medications and Other Restrictions

8.7.1. Concomitant Medications

Maintenance medications as prescribed by their physicians are permitted. All medications (prescription and OTC), vitamin and mineral supplements, and herbs taken during the study will be documented on the concomitant medication case report form (CRF). Information recorded will include: start and stop dates and times, dose and route of administration, and indication. Medications taken for a procedure should also be included.

8.7.2. Other Restrictions

Subjects/patients will be instructed to adhere to the following restrictions:

- Strenuous activity (as assessed by the investigator) is prohibited from 72 hours prior to admission until completion of dosing.
- Subjects/patients are not permitted to consume alcohol from 24 hours prior to admission until completion of dosing.
- Subjects/patients are not permitted to consume any food and drink from outside of the VA during the testing period.
- Subjects/patients must comply with the VA smoking policy, if applicable.
- Subjects/patients are not permitted to participate in any other clinical trial or donate blood or plasma while participating in this clinical trial.

9. STUDY ASSESSMENTS AND PROCEDURES

Subjects/patients will undergo study procedures and assessments at time points specified in the Schedules of Assessments and Procedures ([Table 1](#))

9.1. Medical and Surgical History

The investigator or designee will collect and document a complete medical and surgical history at screening. Medical and surgical history will be collected and documented at test day admission to determine if any changes have occurred since screening. The medical history should include all active medical problems regardless of time of onset.

9.2. Demographic Characteristics

Demographic characteristics including sex, age, race, and ethnicity will be recorded.

9.3. Physical Measurements

Height (cm) and body weight (kg) without shoes will be recorded. Body mass index will be calculated using the height obtained at screening.

9.4. Performance Assessments

Plasma performance samples for determination of PV and GFR will be collected at time points specified in the Performance Sampling Schedules ([Table 2](#)). Concentration of FAST VFI will be determined on the FAST BioMedical Fluorescent Instrument (FBFI). Concentrations of iohexol will be determined via the validated University of Minnesota LC-MS/MS method.

Measurements of PV and ISV will be determined using the FAST BioMedical Technology and mathematical equations.

9.5. Safety Assessments

9.5.1. Adverse Events

Subjects will be monitored for AEs from administration of the first dose of VFI through the follow-up phone call/EOS visit. Refer to [Section 10](#) for additional details.

9.5.2. Clinical Laboratory Tests

The electronic medical record will be used to find the most recent values for the clinical laboratory tests listed in [Table 6](#), all of which are checked with a frequency ranging from twice a month to once a quarter during the routine course of hemodialysis. The baseline laboratory test results for clinical assessment for a particular test will be defined as the last measurement prior to the first dose of VFI.

During the screening period, if a subject/patient has an out-of-range value for a clinical laboratory parameter which the investigator believes is not clinically significant, but the investigator wants to confirm with a repeat laboratory test, a single repeat is allowed to confirm the initial result.

Table 6. Clinical Laboratory Tests	
Hematology	Serum Chemistry
Hematocrit	Sodium
Hemoglobin	Potassium
Red blood cell count	Chloride
Mean corpuscular volume	Albumin
White blood cell count	Alkaline phosphatase
Platelet count (estimate not acceptable)	Glucose
	Total cholesterol
	BUN
	Creatinine
	Total bilirubin
	Calcium
	Total protein
	Phosphorous

For any laboratory test value outside the reference range that the investigator considers clinically significant during the on-study period (ie, following dose administration), the investigator will:

- Repeat the test to verify the out-of-range value and clinical significance.
- Follow the out-of-range value to a satisfactory clinical resolution.
- Record as an AE any laboratory test value that (1) is confirmed by repeat and the investigator considers clinically significant, (2) requires a subject/patient to be discontinued from the study, (3) requires a subject/patient to receive treatment, or (4) requires a change or discontinuation of the study product (if applicable).

9.5.2.1. Kidney Function

- Patients must be on chronic hemodialysis for ≥ 3 months and oliguric defined as ≤ 2 urinary voids per day.

9.5.2.2. Other Tests

A certified laboratory will be utilized to process and provide results for the additional lab tests listed below, to be drawn prospectively for the study unlike the baseline tests listed in [Table 6](#).

- Pregnancy test (nonmenopausal females only)
- nT Pro-BNP

- Creatinine phosphokinase
- Liver function tests: Alanine aminotransferase (ALT), aspartate aminotransferase (AST), and total bilirubin
- Timed Urine Collection (patient arrival to departure on visit 2) for:
 - Total Volume
 - Creatinine
 - Urea Nitrogen

9.5.3. Vital Signs

Vital signs assessments will include oral temperature (°C), respiratory rate (breaths per minute), systolic and diastolic BP (mmHg), and pulse rate (bpm). Blood pressure and pulse rate will be measured after the subject/patient has been resting quietly in a supine position or in the most recumbent position possible for at least 5 minutes.

Vital signs abnormalities that (1) are considered clinically significant initially and on confirmation, (2) require a subject/patient to be discontinued from the study, (3) require a subject/patient to receive treatment, or (4) require a change or discontinuation from the study product (if applicable) will be recorded as AEs.

9.5.4. Physical Examination

Complete physical examinations (including eyes, ears, nose and throat, cardiac, peripheral vascular, pulmonary, musculoskeletal, neurologic, abdominal, lymphatic, and dermatologic systems) will be performed, and abnormal findings will be documented in the subject's/patient's CRF.

An abnormal physical examination finding that is considered clinically significant and (1) requires the subject/patient to be discontinued from the study, (2) requires the subject/patient to receive treatment, or (3) requires a change or discontinuation of the study product (if applicable) will be recorded as an AE.

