10. ADVERSE EVENTS

An AE is defined as any untoward medical occurrence in a subject administered a pharmaceutical product during the course of a clinical investigation. An AE can therefore be any unfavorable and unintended sign, symptom, or disease temporally associated with the use of an investigational product, whether or not thought to be related to the investigational product. Any worsening of the patient's disease under study or other medical conditions will also be considered to be an adverse event, unless it is within the normal range of disease fluctuation for that patient.

An unanticipated adverse device effect (UADE) is any serious adverse effect on health or safety or any life-threatening problem or death caused by, or associated with, a device, if that effect problem, or death was not previously identified in nature, severity, or degree of incidence in the investigational plan, or any other unanticipated serious problem associated with a device that relates to the rights, safety, or welfare of subjects.

Subjects will be monitored throughout the study for AEs, from administration of the first dose of VFI through the follow-up phone call/EOS visit. Adverse events that are identified at the last assessment visit (or the early termination visit) as specified in the protocol must be recorded on the AE CRF with the status of the AE noted. All events that are ongoing at this time will be recorded as ongoing on the CRF. All (both serious and nonserious) AEs must be followed until they are resolved or stabilized, or until attempts to determine resolution of the event are exhausted. The investigator should use his/her discretion in ordering additional tests as necessary to monitor the resolution of such events.

The procedures specified in [Section 10.4](#) are to be followed for reporting SAEs.

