10.2. Assessment of Adverse Events

The investigator will assess each AE for seriousness, intensity, and relationship to study product.

10.2.1.Serious Adverse Events

The investigator is responsible for determining whether an AE meets the definition of an SAE. An SAE is any AE occurring from ICF signing through the follow-up phone call/EOS visit that results in any of the following outcomes:

- Death
- A life-threatening adverse drug experience
- Inpatient hospitalization or prolongation of existing hospitalization
- A persistent or significant disability/incapacity
- A congenital anomaly/birth defect

Important medical events that may not result in death, be life-threatening, or require hospitalization may be considered an SAE when, based upon appropriate medical judgment, they may jeopardize the subject and may require medical or surgical intervention to prevent any of the outcomes listed in this definition. Examples of such medical events include allergic bronchospasm requiring intensive treatment in an emergency room or at home, blood dyscrasias or convulsions that do not result in inpatient hospitalization, or the development of drug dependency or drug abuse.

Note: SAEs require immediate reporting to the sponsor. Refer to “Reporting Serious Adverse Events” (Section 10.4) for details.

10.2.2.Intensity

The intensity of an AE will be graded according to the following definitions:

- Mild: Any symptom of which the subject is aware, but which is easily tolerated; asymptomatic or mild symptoms; clinical or diagnostic observations only; intervention not indicated.
- Moderate: Any symptom which is discomforting enough to cause interference with a subject's usual activity; minimal, local, or noninvasive intervention indicated; limiting age-appropriate instrumental activities of daily living (ADL).
- Severe: Any symptom which causes a subject's inability to perform usual activity; severe or medically significant but not immediately life-threatening; hospitalization or prolongation of hospitalization indicated; disabling; limiting self-care ADL.

It should be noted that a severe adverse event need not be serious in nature and that an SAE need not, by definition, be severe.

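### Section 9.5.4 sets a narrower rule for recording a physical examination finding as an AE than Section 10 and the laboratory and vital-sign rules, and the protocol does not say which governs

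*Protocol*

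**What the plan says.** **Examination rule (Protocol 9.5.4).** All abnormal findings are documented on the CRF. The AE instruction covers the following: "An abnormal physical examination finding that is considered clinically significant and (1) requires the subject/patient to be discontinued from the study", or leads to treatment, or leads to a change or stop of study product. Significance is joined by *and* to a list of three consequences.

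**Laboratory rule (9.5.2).** The instruction begins "Record as an AE any laboratory test value that (1) is confirmed by repeat and the investigator considers clinically significant". Discontinuation, treatment and product change follow as alternatives joined by *or*.

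**Vital-sign rule (9.5.3).** It begins "Vital signs abnormalities that (1) are considered clinically significant initially and on confirmation" and continues with the same three alternatives, again joined by *or*.

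**General definition (Section 10).** "An AE can therefore be any unfavorable and unintended sign, symptom, or disease temporally associated with the use of an investigational product", whether or not it is thought related to the product. No consequence is required.

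**Recording and grading (10.1 to 10.2.3).** Each AE is assessed for seriousness, intensity and relationship to study product. None is an allowed entry for action taken. The Mild grade includes "clinical or diagnostic observations only; intervention not indicated".

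**Analysis (11.3.1 and 11.4).** Examination findings are named in the primary safety endpoint. TEAEs are tabulated as number and percentage of subjects and classified by severity and relationship. Examination findings are listed only.

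**The concern.** AE status decides whether an examination finding enters the summary table or stays in a listing. It also decides whether the investigator must grade intensity and causality and follow the finding to resolution. Section 9.5.4 appears to make that status depend on what was done about the finding, whereas Section 10 makes it depend on what the finding is.

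This matters most for mild signs, which are the least likely to lead to treatment or discontinuation. Section 4.6.2 says that VFI has not previously been given to dialysis patients, and section 4.3 calls for close monitoring for allergic signs. The examination described in 9.5.4 includes the dermatologic system, where such a sign could be seen. A causality grade that was not made at the time cannot readily be restored at analysis.

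**Working it through.** The protocol states no figure on this point that could be reproduced. The check compares the rules and then works out the scale.

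**Step 1. The four rules side by side**

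| Source | Is clinical significance sufficient? | Is a consequence required? |
|---|---|---|
| 9.5.2 Laboratory tests | Yes, if confirmed by repeat | No |
| 9.5.3 Vital signs | Yes, if confirmed | No |
| 9.5.4 Physical examination | No | Yes: discontinuation, treatment or product change |
| Section 10 definition | Not needed; an unfavorable, unintended sign is enough | No |

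Section 9.5.4 is the only row that requires a consequence.

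**Step 2. A test case.** Take a new rash found at examination after dosing, judged clinically significant, not treated, and leading to no change of product or participation.
- Under Section 10 it is an AE. It fits the Mild grade, with action taken entered as none.
- Under 9.5.4 it meets the first condition and none of the three consequences, so that section does not direct that it be recorded as an AE.
- No sentence in the protocol ranks the two sections.

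Both VFI doses fall on Day 1. After the second there is no product left to change, so only discontinuation or treatment could then bring a finding under 9.5.4.

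**Step 3. How often the rule can apply.** AE monitoring starts at the first VFI dose (9.5.1), so only post-dose findings count. Table 1 marks physical examination at Screening and in the Day 1 Dose 1 column, and nowhere under Dose 2, Day 3, Day 8 or Day 31. That is at most one scheduled post-dose examination per subject. The timing of the Day 1 examination relative to injection is not fixed. The note to Table 1 includes physical examination in its recommended order for post-dose procedures, which points to a post-dose examination but does not settle it. Unscheduled examinations could add to the exposure.

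**Step 4. Effect on the TEAE table.** The unit in 11.4 is the subject, and N is about 10.
- If the omitted event is the subject's only TEAE, overall incidence falls by 1/10 = 10 percentage points.
- If the subject has any other TEAE, overall incidence does not change. The preferred-term row still loses 1/10 = 10 points, unless the subject already has that term.

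For scale, the exact (Clopper-Pearson) 95% intervals at N = 10 are:
- 0/10 = 0%: 0 to 30.8%
- 1/10 = 10%: 0.3% to 44.5%
- 2/10 = 20%: 2.5% to 55.6%

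A change of one subject is small against intervals of this width.

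**Step 5. How often would it be the sole TEAE?** The protocol does not say. As an illustration only, suppose the chance that an affected subject has another TEAE equals the overall TEAE proportion in an earlier VFI study (section 4.4.2.1):
- Phase 2a, 19/33 = 57.6%: expected shift per omitted event = 10 × (1 − 0.576) = 4.2 points.
- Phase 2c, 37/50 = 74%: expected shift = 10 × (1 − 0.74) = 2.6 points.

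Those populations differ from this one. No document gives a rate for untreated findings seen only at examination, so the number of omitted events cannot be estimated.

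**The case against.** The strongest reply is that 9.5.4 never says *only*. It names findings that will be recorded as AEs and does not declare that others are not. Section 9.5.1 sends the reader to Section 10, monitoring runs from first dose to the end-of-study contact, and the Mild grade and the action category none show that untreated events are expected. Abnormal findings are on the CRF and in a listing that is easy to read with about 10 subjects. Examinations are few.

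All of this stands, and it limits the point. It does not remove the inconsistency: 9.5.4 omits the stand-alone item that its two sister rules contain, and site staff who follow it as written have a reason not to open an AE record. A listing carries no required intensity or causality grade.

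A reader might infer two stronger claims that the documents do not support.

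- *Untreated reactions in general drop out of the TEAE count.* They do not. Symptoms, signs noticed outside a formal examination, vital-sign changes and laboratory changes reach the AE record by routes that require no treatment. At risk is only a sign found at examination, clinically significant, without any of the three consequences, and handled under 9.5.4 instead of Section 10.
- *The vital-sign rule has a similar gap, because an abnormality that resolves before the confirming reading is not recorded.* Confirmation is an ordinary guard against measurement artefact. Under 9.5.3 a treated change counts through its own item, confirmed or not, and Section 10 still covers an untoward change. Confirmed significance is also the standard against which 9.5.4 is found too narrow here.

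**Conclusion.** The inconsistency is certain on the text: 9.5.4 is narrower than the protocol's own AE definition and narrower than the rules for laboratory values and vital signs, and no order of precedence is given.

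The practical effect is probably small and cannot be estimated. It requires a post-dose examination, a clinically significant sign with none of the three consequences, and a site that reads 9.5.4 as the controlling rule. If all three occur, the finding is listed without required intensity or causality grading and is missing from the TEAE table. At N = 10, overall incidence moves by 10 points per affected subject if that was the subject's sole TEAE, and otherwise by nothing. The correction is worth making because the contradiction is plain and cheap to remove, not because a large bias is expected.

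**What to change.** Make one of two changes.

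1. Reword 9.5.4 so that any new or worsened examination finding after the first dose that the investigator considers clinically significant is recorded as an AE, whether or not it leads to discontinuation, treatment or a product change.
2. Or keep the present sentence and add that the Section 10 definition governs wherever 9.5.4 is narrower.

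The first is preferable, because site staff will use 9.5.4 when they complete the examination page. Section 9.5.3 needs no change.

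The cost is one sentence in the protocol and the matching CRF instruction. The downside is a few more mild AEs recorded.
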